6.2 Clinical Condition/Indication

Graft-versus-host disease is one of the most common complications of allogeneic hematopoietic stem cell transplantation (HSCT), a component of a treatment program for blood cancer and other blood disorders. Despite prophylactic treatment with immunosuppressive agents, acute GvHD occurs in 30% to 70% of patients undergoing HSCT and is associated with significant morbidity and mortality. Severe GI acute GvHD is estimated to have a mortality rate as high as 70% to 80%.⁸ Standard, frontline therapy for acute and chronic GvHD consists of glucocorticoids, but less than 40% of patients treated with steroids have durable complete responses (CRs) or PRs, a complete or partial resolution of all signs and symptoms of GvHD in all organs.^{9;10} The 1-year survival rate for subjects who do not respond to steroid therapy ranges from 5% to 30%.^{8;9;11;12,13,14} There is currently no FDA-approved treatment for acute GvHD.

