9. SUBJECT SELECTION, WITHDRAWAL, AND DISCONTINUATION

9.1 Inclusion Criteria

Subjects who meet **ALL** of the following criteria are eligible for Parts 1 and 2 of this study:

1. Male or female subjects aged ≥ 18 years at the time of screening
2. Recipient of an HSCT
3. The disease indication for which the subject required HSCT must be in remission
4. Newly diagnosed acute GvHD, including lower GI involvement (modified International Bone Marrow Transplant Registry [IBMTR] Severity Stage 1 to 4 [>500 mL diarrhea/day]), with or without other organ system involvement.
5. Willing to undergo or must have had a lower GI biopsy within 7 days of informed consent to confirm GI GvHD. Biopsy results are not needed to initiate treatment; however, if biopsy results are not consistent with aGvHD, treatment with GLASSIA will be discontinued.
6. Subjects must be receiving systemic corticosteroids. Treatment with methylprednisolone/systemic steroids must have been initiated within 72 hours prior to the first dose of study treatment after enrollment.
7. Evidence of myeloid engraftment (absolute neutrophil count $\geq 0.5 \times 10^9/L$)
8. Lower GI GvHD manifested by diarrhea must have other causes of diarrhea ruled out (eg, negative for *Clostridium difficile* or cytomegalovirus [CMV] infection or oral magnesium administration)
9. Karnofsky Performance Score $\geq 50\%$ ²⁹
10. If female of childbearing potential, subject presents with a negative blood pregnancy test
11. Females of childbearing potential with a fertile male sexual partner must agree to employ adequate contraception for the duration of the study. Adequate contraception is defined as using hormonal contraceptives or an intrauterine device combined with at least 1 of the following forms of contraception: a diaphragm, cervical cap or a condom
12. Males must use adequate contraception and must not donate sperm for the duration of the study. Adequate contraception for the male subject and his female partner is defined as using hormonal contraceptives or an intrauterine device combined with at least 1 of the following forms of contraception: a diaphragm, cervical cap or a condom
13. Subject is willing and able to comply with the requirements of the protocol

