11.12 Mortality and Survival Assessments

All-cause, transplant-related, infection-related and GvHD-related mortality will be calculated as the time from HSCT to death; the cause of death will be based on the investigator's assessment. The date and cause of death, if applicable, will be collected in the eCRF at the visits indicated in Table 1. The following definitions will be used by the investigator to assess the cause of death. These categories are not mutually exclusive, and the investigator will select all applicable categories:

- Transplant-related mortality: death related to transplantation (including deaths related to GvHD)
- Infection-related mortality: death related to infection (including infections related to HSCT)
- GvHD-related mortality: death related to GvHD
- Other cause: any death not related to transplant, infection or GvHD

Failure-free survival, GvHD-free survival and overall survival will be collected in the eCRF at the visits indicated in Table 1.

Failure-free survival is determined by the investigator and defined as the absence of all 3 of the following criteria:

- Need for second-line treatment for acute GvHD
Second-line treatment is defined as any additional systemic treatment used for steroid nonresponsive treatment of acute GvHD. Methylprednisolone (or equivalent steroid) doses greater than 2 mg/kg/day required for the treatment of GvHD will also be considered second-line therapy

- Non-relapse mortality
Non-relapse mortality is defined as death during continuous complete remission
- Recurrent malignancy

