12.11 Recurrent Malignancy

At screening and all visits during the study, subjects will be assessed for recurrent malignancy. Recurrent malignancy must be confirmed by a biopsy, per standard institutional practice. The investigator will record the presence or absence of recurrent malignancy in the eCRF.

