This SAP is for Part 1 of the 2-part study and is based on the original protocol and thus documents all derivations of outcome variables, statistical analyses and summaries preplanned in the original protocol. Derivations of outcome variables, statistical analyses and summaries in this SAP are no longer applicable, as indicated by “Not Applicable” in the appropriate sections, but the analysis content is retained only for alignment with the original protocol. Only data listings will be produced for the single-enrolled subject, and the listings will include raw (actual) values. In addition, since no adjudication of the response assessment data will be done, only the data based on the investigators’ assessments will be presented in the listings.

There will be no SAP for Part 2 since the entire study (Part 1 and Part 2) was terminated before start of Part 2. No subjects were enrolled in Part 2 at time of termination.

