first dose of study treatment until death due to the corresponding cause, in the presence of other mortality causes. Any subject not having death will be censored at the date of study completion/early termination (or the last recorded date during the study). For time to transplant-related mortality, subjects having death due to a reason other than transplant-related will be censored at the date of death, and handled differently in the estimation from the censoring not due to a competing cause. Time to infection-related mortality and time to GvHD-related mortality will be censored for subjects without an event in a similar fashion. The probability of transplant-related, infection-related and GvHD-related mortality at Days 28, 56, 100 and 180 will be estimated using the competing risk estimate of cumulative incidence function. GvHD-related mortality will also be presented using a cumulative incidence rate plot.

Failure-free survival at Days 100 and 180

Failure-free survival is defined as the time from the first dose date of study treatment until death or the first date of failure-free survival not achieved (CRF Mortality and Survival Assessments [MORTAL] module), whichever comes earlier. The failure-free survival are determined by investigator with the absence of all 3 of the following criteria:

- Need for second-line treatment for acute GvHD. Second-line treatment is defined as any additional systemic treatment used for steroid nonresponsive treatment of acute GvHD. Methylprednisolone (or equivalent steroid) doses greater than 2 mg/kg required for the treatment of GvHD will also be considered second-line therapy
- Non-relapse mortality. Non-relapse mortality is defined as death during continuous complete remission
- Recurrent malignancy

Subjects without recorded death and failure-free survival not achieved at any survival and mortality assessment will be censored at the date of last mortality and survival assessment.

Failure-free survival will be summarized at Days 100 and 180 using the same approach (Kaplan-Meier) as described for overall survival.

GvHD-free survival at Days 28, 56, 100 and 180

GvHD-free survival is defined as the time from the first dose date of study treatment until death or the first date of GvHD-free survival not achieved (CRF MORTAL module), whichever comes earlier. Subjects without recorded death and GvHD-free survival not

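### Protocol 11.12 does not count every death as a failure-free survival event, and no document supplies a rule for Part 2 that does

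*Protocol*

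**What the plan says.** Protocol 11.12 sets the rule: "Failure-free survival is determined by the investigator and defined as the absence of all 3 of the following criteria". The first criterion is "Need for second-line treatment for acute GvHD", which includes steroid doses above 2 mg/kg/day given for GvHD. The second is non-relapse mortality, and the third is recurrent malignancy. Death enters only through the second: "Non-relapse mortality is defined as death during continuous complete remission".

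Three other places in the protocol affect who can meet that definition.
- Inclusion criterion 3 (9.1): "The disease indication for which the subject required HSCT must be in remission". Remission is not defined and is not required to be complete.
- Section 12.11: "Recurrent malignancy must be confirmed by a biopsy, per standard institutional practice".
- Section 6.2 describes transplantation as "a component of a treatment program for blood cancer and other blood disorders". No eligibility criterion requires a malignant indication.

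Failure-free survival at Days 100 and 180 is eighth of the twelve other secondary efficacy measures in 8.4.2.1. Section 13.4.2 compares it between arms in Part 2 with a Cox model. It gives no event or censoring rule of its own.

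SAP 7.2.2 repeats the three criteria with the same wording on non-relapse mortality, but measures time from first dose "until death or the first date of failure-free survival not achieved (CRF Mortality and Survival Assessments [MORTAL] module), whichever comes earlier". It censors only subjects with neither a recorded death nor a recorded failure. The SAP covers Part 1. Its introduction says "There will be no SAP for Part 2", because the study was terminated before Part 2 began.

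**The concern.** In an endpoint named failure-free survival, one expects every death to be an event. The three protocol criteria do not ensure this. Deaths after second-line treatment or confirmed recurrence are already failures, so the gap concerns only deaths that are the subject's first event. Among these, the criteria catch a death in continuous complete remission and are silent on any other.

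At stake is the event definition for a randomised secondary comparison. If the criteria were applied as written, some dead subjects could be carried as failure-free or censored at death, and the failure-free proportion would be too high. Because the investigator determines the status, two sites could also score similar deaths differently.

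**Working it through.** The documents give no rate, power or sample size for failure-free survival, so there is no planned figure to reproduce. The check is a reading of the text, followed by an illustration of size.

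**Step 1: first-event deaths under each rule.** In every case there was no second-line treatment and no biopsy-confirmed recurrence before death.

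| Status at death | Protocol 11.12 | SAP 7.2.2 (Part 1) |
|---|---|---|
| Continuous complete remission | Event | Event |
| In remission at entry, but not complete remission | Meets no criterion | Event |
| Transplanted for a non-malignant disorder | Ambiguous | Event |
| Clinical relapse, never biopsied | Ambiguous | Event |

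The second row is the firm case, because inclusion criterion 3 does not ask for complete remission. The third row is ambiguous because the protocol does not say what remission means for a non-malignant disorder. If the term can be applied, the death can count. The fourth row is ambiguous because an unconfirmed relapse can be read as remission continuing (the death counts) or as remission interrupted (it does not).

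**Step 2: size.** Let d be the share of subjects who die as a first event and q the share of those deaths outside continuous complete remission. If the missed deaths are carried as failure-free:

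overstatement = d × q

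Neither input is in the documents. Assumed ranges are d = 10% to 40% and q = 0% to 30%.

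| d | q | Overstatement (points) | Of 74 subjects per arm |
|---|---|---|---|
| any | 0% | 0.0 | 0.0 |
| 10% | 10% | 1.0 | 0.7 |
| 20% | 20% | 4.0 | 3.0 |
| 30% | 20% | 6.0 | 4.4 |
| 40% | 30% | 12.0 | 8.9 |

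For the last row, 0.40 × 0.30 = 0.12 and 74 × 0.12 = 8.9. If the missed deaths were instead censored at death, the Kaplan-Meier overstatement would be no larger than d × q. The protocol does not say which would apply.

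**Step 3: direction between arms.** The difference in overstatement is (d × q in the GLASSIA arm) − (d × q in the control arm). Take q = 20% in both arms.
- With d = 30% on GLASSIA and 20% on control, it is 6.0 − 4.0 = 2.0 points in favour of GLASSIA. This could arise if GLASSIA reduced second-line use with mortality equal, so that more of its deaths were first events.
- With the two values of d exchanged, it is 4.0 − 6.0 = −2.0 points, against GLASSIA. This could arise if GLASSIA prevented the deaths that the rule omits.
- With no treatment effect on any component, the expected difference is zero.

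**The case against.** The strongest reply is that no document derives the endpoint in a way that scores a dead subject as failure-free. The only derivation, SAP 7.2.2, sets the narrow criteria beside an any-death rule. This suggests that its authors took the criteria to define a case report form field and handled death separately. On that view the protocol is incomplete rather than in conflict with the SAP. Nor does the lack of a Part 2 SAP show that Part 2 would have been analysed without such a rule, since it follows from termination. Much of this stands. A reader might infer that dead subjects would be counted as successes in Part 2, but the documents do not establish that. They show only that the protocol's criteria allow it and that nothing written for Part 2 prevents it.

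A reader might also infer that deaths in non-malignant disease and after unbiopsied relapse are certainly missed. That does not stand either, because each can be read so that the death counts. They are evidence of unclear wording, not further proven gaps.

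Finally, no death would be hidden from the report. Overall survival and all-cause mortality are separate endpoints, date of death is collected, and 11.13 provides for adjudication of all efficacy data. This limits the consequence but does not supply the missing event rule.

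**Conclusion.** The point holds in limited form. As written, protocol 11.12 leaves out a first-event death in a subject who is not in complete remission, and it is ambiguous for two other kinds of death. Part 1 is covered by the SAP; Part 2 is not covered by any document.

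The size is unknown. The range of 0 to 12 points (0 to about 9 of 74 subjects per arm) rests wholly on the assumed shares, and its lower end applies if every first-event death is judged to be in continuous complete remission. It is tempting to conclude that the rule favours GLASSIA. The documents do not support that, because the sign depends on treatment effects they cannot tell us.

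Severity is low. The endpoint is secondary and the correction is one of wording. The SAP records termination with one subject enrolled in the study and none in Part 2, so the defect is in the plan and affects no Part 2 result.

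**What to change.** In protocol 11.12, and for the Part 2 analysis in 13.4.2, define the failure-free survival event as the first of second-line treatment for acute GvHD, recurrent malignancy, or death from any cause. This matches how SAP 7.2.2 treats death.

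If non-relapse mortality is to remain a named component, define it as death without prior recurrent malignancy, using the biopsy-confirmed meaning in 12.11. That also closes the gap, because death after recurrence is already a failure, and it settles the two ambiguous cases.

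The cost is about one sentence in each section. No new data are needed, since date of death is already collected. The failure-free estimate falls by whatever share was being missed.

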11.13 Adjudication Committee

An adjudication committee will review and adjudicate all efficacy data prior to statistical analysis. During Part 2 of the study, the committee will be blinded to study treatment assignment, until the committee has adjudicated all data through Day 56 and the study has been unblinded. The committee will be composed of experts in the fields of oncology, hematology or immunology who specialize in HSCT and are not participating as investigators in the study. The experts will adjudicate all efficacy data in both parts of the study. Adjudication of Part 1 efficacy data will not be required prior to initiating Part 2 of the study.

The adjudication committee's responsibilities, definitions and operating procedures will be defined in a charter; the committee will maintain records of all its meetings.

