8. STUDY DESIGN

8.1 Brief Summary

This is a 2-part Phase 2/3, prospective, controlled, randomized, multicenter study in subjects with acute GvHD with Stage 1 to 4 lower GI involvement. Part 1 will be a nonrandomized, open-label, active treatment, multicenter study to evaluate the safety, efficacy and PK of GLASSIA in approximately 20 evaluable subjects. Part 2 will be a randomized, parallel-group, double-blind, multicenter study to compare the safety and efficacy of GLASSIA versus albumin (control) in a total of 148 randomized subjects (74 subjects/group).

Eligible subjects for Parts 1 and 2 must be recipients of an allogeneic HSCT and have been newly diagnosed with acute GvHD with Stage 1 to 4 lower GI involvement (modified IBMTR).^{15;16} Subjects must have evidence of myeloid engraftment. There are no restrictions on the prior conditioning treatments. Subjects may continue any prior therapy used for prophylaxis (eg, cyclosporine and/or mycophenolate mofetil) at a stable dose from baseline if the therapy agent was not discontinued and restarted after initiating first-line steroid treatment for acute GvHD. Subjects may have been treated with corticosteroids for acute GvHD with lower GI involvement for a maximum of 72 hours prior to initiation of GLASSIA administration.

All eligible subjects in Parts 1 and 2 will be given 2 mg/kg/day of methylprednisolone or equivalent steroid (either IV or oral per investigator discretion) and IV study treatment (defined as GLASSIA in Part 1; GLASSIA or control in Part 2). Steroids will be tapered as appropriate, according to institutional practice and guidance provided in Section 8.2.

Results from Part 1 will be used to determine whether continuation to Part 2 is warranted. All efficacy data will be adjudicated by an Adjudication Committee (Section 11.13).

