8.5.2 Blinding

The solutions for GLASSIA and albumin (control) in Part 2 will be identical in volume, color and foaming characteristics. Blinding of the study treatment will be performed by an unblinded pharmacist at the study site, who will also prepare the study treatment for administration.

An independent, unblinded biostatistics team will perform the interim analysis of Part 2 and will present the results to the DMC (Section 13.5).

The treatment each subject receives will not be disclosed to the investigator, study site staff, subject, sponsor or contract research organization, including at the interim analysis of Part 2, unless the subject meets criteria for unblinding (Section 8.5.3).

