8.5.3 Unblinding

The process for breaking the blind in Part 2 will be handled through the IRT. Investigators are strongly discouraged from requesting the blind be broken for an individual subject, unless there is a subject safety issue that requires unblinding and would change subject management. Any site that breaks the blind under inappropriate circumstances may be asked to discontinue its participation in the study. If the blind is broken, it may be broken for only the subject in question.

The sponsor and the contract research organization must be notified immediately if a subject and/or investigator is unblinded during the course of the study. Pertinent information regarding the circumstances of unblinding of a subject's treatment code must be documented in the subject's source documents and electronic case report forms (eCRFs).

The study will be unblinded after all subjects complete Day 56 of Part 2 or discontinue study treatment and the Adjudication Committee adjudicates all efficacy data through Day 56 of Part 2 (Section 11.13).

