20. SUPPLEMENTS

20.1 Study Flow Chart

[figure not shown]
Figure 1
Study Design for Baxalta Clinical Study 471501 Part 1

Abbreviations: SOC=standard-of-care.

Note: Arrows indicate days of study treatment and the Day 28 primary endpoint assessment.

Figure 2
Study Design for Baxalta Clinical Study 471501 Part 2

Abbreviations: R=randomization; SOC=standard-of-care.

Note: Arrows indicate days of study treatment and the Day 28 primary endpoint assessment. The study will be unblinded after all subjects complete Day 56 of Part 2 or discontinue study treatment and the Adjudication Committee adjudicates all efficacy data through Day 56 of Part 2.

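### The protocol lets the adjudication committee's blind end at the Day 56 unblinding, although the committee must still adjudicate later efficacy data, chiefly duration of response

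*Protocol*

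**What the plan says.** On scope, Protocol Section 11.13 opens with "An adjudication committee will review and adjudicate all efficacy data prior to statistical analysis" and adds "The experts will adjudicate all efficacy data in both parts of the study". Section 8.1 repeats it: "All efficacy data will be adjudicated by an Adjudication Committee". None of these stops at Day 56.

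On the committee's blind in Part 2, Section 11.13 says that "the committee will be blinded to study treatment assignment, until the committee has adjudicated all data through Day 56 and the study has been unblinded". It leaves the committee's operating procedures to a charter.

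On the trigger, Section 8.5.3 says "The study will be unblinded after all subjects complete Day 56 of Part 2 or discontinue study treatment and the Adjudication Committee adjudicates" its efficacy data through Day 56. The Figure 2 note in Section 20.1 matches: "The study will be unblinded after all subjects complete Day 56 of Part 2 or discontinue study treatment", with the same adjudication condition. Neither names the roles that are unblinded.

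On other roles, Section 8.5.2 says "The treatment each subject receives will not be disclosed to the investigator, study site staff, subject, sponsor or contract research organization", with the exception "unless the subject meets criteria for unblinding (Section 8.5.3"). It gives no end date and does not list the committee.

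On later outcomes, Table 1 (Section 20.2) schedules overall and GI response at Days 100 and 180. Section 13.4.2 analyses duration of both responses by Cox model. Section 13.4 places the primary analysis after the Day 56 unblinding and a final secondary analysis after study completion.

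**The concern.** A blinded committee protects an endpoint that rests on judgment. The end of a response depends on deciding when GvHD has progressed, so knowledge of the arm could move that date. The protocol asks the committee to keep adjudicating after the point at which its blind is no longer guaranteed.

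There is a second gap. Data through Day 56 must be adjudicated before unblinding. Later data already collected by then need only be adjudicated before analysis. Nothing says this must come before unblinding.

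At stake is the comparison of duration of overall and GI response, both secondary outcomes.

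**Working it through.** **1. Which later outcomes run through the committee.**

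| Outcome after Day 56 | Who assesses it | Shown on adjudicated data? |
|---|---|---|
| Duration of overall and GI response | Investigator at Days 100 and 180 (Section 11.5, Table 1), then committee | Yes, beside investigator data (SAP 7.2.2; Part 1 only, so indirect) |
| Acute GvHD grade, Day 180 | Investigator (Section 11.4) | No, investigator staging in SAP 7.2.2 |
| Chronic GvHD to Day 365 | Investigator (Section 11.6) | No |
| Failure-free survival, cause of death | Investigator (Section 11.12) | No |

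Duration of response is therefore the outcome mainly exposed to an unblinded committee. For the investigator-assessed outcomes the question is mainly whether the study-level unblinding reaches investigators.

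**2. The plan's own timetable.** The Synopsis puts primary completion at 2018 SEP and study completion at 2019 JUL: 274 to 333 days apart, depending on the day of the month. Day 365 minus Day 56 is 309 days, inside that range. The plan thus contains about 10 months of follow-up after its primary completion date.

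**3. Part 2 accrual time (A), not stated and so derived.** From 2016 OCT to 2018 SEP, less 56 days for the last subject to reach Day 56, leaves 614 to 673 days. Subtract 28 days for the wait between Part 1 and Part 2: 586 to 645. Take Part 2's share of the 168 planned subjects (20 + 148):

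- 586 × 148/168 = 516 days
- 645 × 148/168 = 568 days

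This assumes the same accrual rate in both parts.

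**4. Share not yet at Day d when the study is unblinded.** Assume uniform accrual, a last subject who reaches Day 56, and an adjudication lag L of 30 to 60 days (assumed). Then share = max(0, d − 56 − L)/A.

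- Day 180, low: 64/568 = 11%, or 17 of 148
- Day 180, high: 94/516 = 18%, or 27 of 148
- Day 100, low (L = 60): 0
- Day 100, high: 14/516 = 3%, or 4 of 148

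Of the 2 × 148 = 296 response readings scheduled after Day 56, 17/296 to (27 + 4)/296 fall after unblinding, about 6% to 10%.

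**5. Sensitivity for Day 180.**

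- A of 365 days (assumed), L = 30: 94/365 = 26%, or 38 subjects
- No lag, a limiting case: 124/568 to 124/516 = 22% to 24%
- Two-year recruitment from Section 8.3, less the 28-day gap: 702 × 148/168 = 618 days, so the low end is 64/618 = 10%
- A trigger reached earlier through treatment discontinuation adds about 0.2 points per day (1/568 to 1/516)

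**6. Fewer contribute to duration of response.** Only responders count. At the planning rates of 40% and 65% (Section 13.1; mean 52.5%), 17 to 27 subjects become about 9 to 14. This is only a guide: those rates are for Day 28, response at any visit counts, and some responders will already have progressed or died. Section 10.6 also ends later visits for subjects who stop study treatment. If 10% to 60% stop (assumed), 17 to 27 subjects become 15 to 24 at 10% and 7 to 11 at 60%, before the responder reduction. Section 8.2 says instead that all subjects are followed to Day 365; the two sections must be reconciled.

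**7. The other extreme.** Steps 4 to 6 assume that data collected before unblinding are also adjudicated before it. If the committee takes up post-Day 56 data only after unblinding, all of those data could be adjudicated with the arm known.

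**The case against.** The strongest reply is that Section 11.13 ends a guarantee and does not say that the committee receives the codes. The charter may keep it blinded. This stands, and it is why the point is what the protocol permits. A reader might infer that every later efficacy outcome will be adjudicated unblinded. The documents do not support that: the charter is unseen, and most later outcomes are investigator-assessed.

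A reader might also infer that investigators, site staff and subjects learn the assignments at the Day 56 milestone. Section 8.5.2 most naturally says otherwise. Its exception applies when a subject meets criteria, which fits the individual safety code break; a study milestone is not something that a subject meets. What remains is that Section 8.5.3 also holds the study-level unblinding and names no roles, and that Section 8.5.2 groups the sponsor and contract research organization with the sites. That calls for reconciliation and does not establish that sites are unblinded.

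Finally, unblinding at a prespecified primary analysis is a declared choice, and in the Part 1 SAP adjudicated data serve only as a sensitivity analysis for the primary endpoint (SAP 7.1). Both are fair. Neither gives a reason to let the committee's own blind lapse while it has data left to adjudicate.

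**Conclusion.** The point holds as a gap in the protocol's guarantee: Section 11.13 allows post-Day 56 response data to be adjudicated with the arm known, and duration of overall and GI response is the outcome mainly exposed. About 11% to 18% of subjects (17 to 27 of 148) would not have reached Day 180 at unblinding, and up to 26% with a 365-day accrual. These figures rest on uniform accrual, a derived accrual time and an assumed lag. The number that matters for duration of response is smaller, unless adjudication of all post-Day 56 data waits until after unblinding.

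Primary, key secondary and Day 56 response are adjudicated blind. Overall survival and all-cause mortality do not depend on this judgment. SAP Section 1 records that the study was terminated with no subject enrolled in Part 2, so no result was touched. This is a cheap improvement for any restart or reuse of the design.

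**What to change.** Amend Section 11.13 and the charter so that the committee stays blinded to treatment assignment until it has adjudicated all efficacy data, including data after Day 56. State in Section 8.5.3 and the Figure 2 note which roles are unblinded at the primary analysis, consistent with Section 8.5.2.

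The cost is wording in two sections, one figure note and the charter. Subject-level codes must also be withheld from the committee for about 10 more months (2018 SEP to 2019 JUL). No subjects or visits are added, and the primary analysis date and individual safety unblinding stay as they are. Keeping sites and subjects blinded to final database lock is an optional further step with its own trade-offs, and is not needed to close this gap.
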